## 1.2. Data Summary

CCI

CCI

To assess the general toxicity profile of DS-2325a, two 4-week intermittent SC dose toxicity studies were conducted, one in mice (CCI) and one in cynomolgus monkeys (CCI), with an 8-week recovery period at the dose levels of 0 (control group), CCI. A 26-week intermittent SC dose toxicity study was also conducted in mice (Q2D, 91 times in total) with an 8-week recovery period at the dose levels of 0 (control group), CCI. In all these studies, no toxicologically significant changes were noted in any animal at dose levels up to CCI included. Therefore, the no observed adverse effect level (NOAEL) of DS-2325a in these studies was considered to be CCI. Additionally, in telemetered male cynomolgus monkeys treated with a single SC dose of DS-2325a, no effects on the cardiovascular system, the respiratory system or the central nervous system were observed at dose levels up to CCI included.

In a cytokine release assay using human peripheral blood mononuclear cells in solid phase, DS-2325a induced higher levels of TNF compared with vehicle control. The extent of induction was less than that of bevacizumab, a reference antibody, for which low incidence of infusion-related reactions has been reported. In cytokine release assays using human peripheral blood mononuclear cells or human whole blood in liquid phase, DS-2325a did not induce the release of any cytokine tested compared with vehicle control. DS-2325a did not show cell proliferation activity in any assay. Therefore, the risk of infusion-related reactions upon DS-2325a administration is considered to be low given the results of these assays.

For further details, please refer to the current Investigator's Brochure (IB).

### 1.3. Study Rationale

Netherton Syndrome is caused by loss-of-function mutations in the gene coding for LEKTI. LEKTI is the natural inhibitor of KLK5, and its functional loss leads to excessive activation of KLK5. DS-2325a may be an ideal pharmacological remedy for NS pathological defect because of its ability to inhibit KLK5. DS-2325a may replace deficient LEKTI in patients with NS and thus block disease development.

DS-2325a is undergoing 2 Phase 1a studies in healthy subjects (HS): 1) a single ascending dose study (SAD), in which DS-2325a is being investigated through SC (6 dose levels ranging from 30 to 1500 mg) and intravenous (IV) (2 dose levels, ie, 100 and 1000 mg) administration; and 2) a multiple ascending dose study, during which DS-2325a is being investigated through SC administration 4 times once a week (3 dose levels, ie, 300, 600, and 900 mg).

This Phase 1b/2 study will initially explore the safety, pharmacokinetics (PK), and efficacy of DS-2325a in adult patients with NS. If found of adequate safety and efficacy, DS-2325a will later be explored also in pediatric patients with NS. The study will follow DS-2325a Phase 1a studies in HS. It will be articulated into an Observational Part, during which patients will receive no treatment, an Interventional Part, during which patients will receive DS-2325a, and a Follow-Up. The Interventional Part will be in turn articulated into 2 phases: A double-blind, placebo-controlled, randomized, parallel-arm Main Phase, during which patients will receive

DS-2325a or placebo, and an open-label Extension Phase, during which all patients will receive DS-2325a. The Interventional Part Main Phase, the core component of the study, will be immediately and seamlessly preceded by the Observational Part and will be followed, also immediately and seamlessly, by the Interventional Part Extension Phase, as long as early clinical signal (ECS), as initial evidence of efficacy, is found at the end of the Main Phase and warrants study continuation. All patients will transition from the Main Phase to the Extension Phase; however, the latter will be discontinued if ECS is not found. After an initial (“loading”) dose of 1000 mg IV, which will be given only in Interventional Part Main Phase, DS-2325a will be given weekly at the maximum feasible dose of 600 mg SC. Both doses were determined to be safe and well tolerated in Phase 1a. DS-2325a is not expected to pose any concerning safety risks, given the results of the toxicology studies and the preliminary results of the Phase 1a studies, but is expected to give initial evidence of efficacy, ie, ECS. This evidence will be based on impact on the Ichthyosis Area Severity Index (IASI) as the main clinical endpoint and on several mechanistic endpoints.

#### **1.4. Dose Selection and Justification of Dose**

CCI

This dosing regimen was found to be safe and well tolerated in Phase 1a. Two Phase 1a studies investigated DS-2325a in HS: A SAD study and a multiple ascending dose (MAD) study. In SAD study, DS-2325a was given to eight cohort of 8 subjects each, randomized 6 to 2 to DS-2325a and placebo, at the SC doses of 30, 100, 300, 600, 1000, and 1500 mg and at the IV doses of 100 and 1000 mg. In MAD study, DS-2325a was given four times once a week to two cohorts of 8 subjects each, also randomized 6 to 2 to DS-2325a and placebo, at the SC doses of 300 and 600 mg. Based on the review of preliminary blinded safety data from these Phase 1a studies, DS-2325a is found to be well tolerated by the study subjects at single SC (up to 1500 mg) and IV (up to 1000 mg) doses and at the multiple SC dose of 300 and 600 mg. The adverse events (AEs) reported in these studies were mild in nature with no serious events reported. Additional information on these AEs is provided in the IB.

CCI

It should be noticed that both in mice and monkeys NOAEL corresponded to the maximum dose tested, since no dose level was found that resulted in toxicities. CCI

CCI

The rationale for the use of placebo is the provision of treatment control, necessary to interpret DS-2325a activity, including safety and tolerability, not only efficacy, even if the sample size of this study was not calibrated to allow finding a statistically significant difference between DS-2325a- and placebo-treated patients at pre-stipulated levels of probability and power.

## 1.5. Risks and Benefits for Study Patients

### Risk Assessment

Based on the nonclinical findings, it is expected that DS-2325a will be safe and well tolerated and will show ECS as initial evidence of efficacy. During this study, there may be risks related to the blood sampling (eg, bruising and pain at the blood draw site). More detailed information about the known and expected benefits and risks and reasonably expected AEs related to DS-2325a may be found in the IB.

## **Coronavirus Disease 2019**

During special circumstances (eg, coronavirus disease 2019 [COVID-19] pandemic), the specific guidance from local public health and other competent authorities regarding the protection of individuals' welfare must be applied.

## **Risk Mitigation Strategies**

The safety monitoring practices employed by this protocol (ie, AEs, clinical laboratory findings, vital signs, 12-lead electrocardiograms (ECGs), and physical findings) are considered adequate to protect the safety of study patients.

All study activities at the study site will be performed by trained clinical staff authorized by the study investigator.

The Sponsor will immediately notify the investigator if any additional safety or toxicology information becomes available during the study.

This study will be performed in compliance with the protocol, International Council for Harmonisation (ICH) Good Clinical Practice (GCP) and applicable regulatory requirements. Aspects of the study concerned with the investigational medicinal product(s) will meet the requirements of European Union – Good Manufacturing Practice.

## **Benefit Assessment**

By receiving DS-2325a, patient's NS condition might improve.

All patients will undergo a physical medical examination at the first study visit; these evaluations, made by skilled and trained clinical staff, may potentially provide valuable knowledge about the patient's health. In case the study staff discovers any medical condition, the patient may be referred to the local healthcare system in case any abnormalities/diseases are observed.

The patients will contribute to the process of developing therapies in an area of unmet need. They may also help provide valuable data, about the tolerability and immunogenicity of DS-2325a and about its potential ability to provide treatment for NS.

## **Overall Risk/Benefit Conclusion**

Considering the measures taken to minimize possible risks to the patients in this study, the potential risks associated with the study drug and study assessments are balanced by the potential benefits that may be provided to the patients.

## **2. STUDY OBJECTIVES, HYPOTHESIS, AND ENDPOINTS**

### **2.1. Study Objectives**

#### **2.1.1. Observational Part Objectives**

To explore the characteristics of patients with NS for 12 weeks immediately before study treatment administration by assessing the same safety and efficacy (including mechanistic efficacy) endpoints to be assessed during the Interventional Part.

#### **2.1.2. Interventional Part Objectives**

##### **2.1.2.1. Primary Objectives**

The primary objective of this study is to explore the safety and tolerability of DS-2325a in patients with NS by administering DS-2325a every other week for 12 consecutive weeks (Main Phase) and to confirm by administering for an additional 24 weeks (Extension Phase).

##### **2.1.2.2. Secondary Objectives**

The secondary objectives of the study are:

- To explore the PK properties of DS-2325a in patients with NS by administering DS-2325a every other week for 12 consecutive weeks (Main Phase) and to confirm by administering for an additional 24 weeks (Extension Phase).
- To explore the efficacy of DS-2325a in patients with NS by administering DS-2325a every other week for 12 consecutive weeks (Main Phase) and to confirm by administering for an additional 24 weeks (Extension Phase).
- To explore the immunogenicity of DS-2325a in patients with NS by administering DS-2325a every other week for 12 consecutive weeks (Main Phase) and to confirm by administering for an additional 24 weeks (Extension Phase).

##### **2.1.2.3. Exploratory Objectives**

The exploratory objectives of the study are:

- To explore the mechanistic efficacy of DS-2325a in patients with NS by administering DS-2325a every other week for 12 consecutive weeks (Main Phase) and to confirm by administering for an additional 24 weeks (Extension Phase).

### **2.2. Study Hypotheses**

It is hypothesized that DS-2325a will be safe and well tolerated and will show ECS as initial evidence of efficacy.

## **2.3. Study Endpoints**

### **2.3.1. Primary Endpoint**

The primary endpoints of this study are:

- Safety endpoints, ie, AEs, including serious AEs (SAEs), injection site reactions (ISRs) physical examination findings, vital sign recordings (body temperature, blood pressure, heart rate, respiratory rate), results of safety laboratory analyses of blood and urine, and ECG findings.

### **2.3.2. Secondary Endpoints**

The secondary endpoints of this study are:-

- Endpoints descriptive of plasma PK properties will be PK parameters derived from population PK analysis, including, but not limited to, pre-dose trough concentration ( $C_{\text{trough}}$ ),  $AUC_{\text{tau,ss}}$ , total body clearance (CL), and CL/F, and epidermis-to-dermis DS-2325a concentration ratio ( $K_{\text{ed}}$ ).
- DS-2325a presence will be assessed in the skin if the optional skin biopsies will be available.
- Several endpoints for the assessment of efficacy (ECS), including, but not limited to IASI (including IASI-Erythema and IASI Scaling), Investigator Global Assessment (IGA) and patient-reported outcome (PRO) measures, such as Itch Numerical Rating Scale (NRS) scores and quality-of-life assessments obtained using the Skindex-29 and the Dermatology-Life-Quality-Index (DLQI) questionnaires.
- Anti-drug antibodies (ADAs) against DS-2325a as the immunogenicity endpoint.

### **2.3.3. Exploratory Endpoints**

The exploratory endpoints of this study are:

- Endpoints for the assessment of mechanistic efficacy, including transepidermal water loss; skin concentration of mediators of skin inflammation and homeostasis, such as S100A7, S100A8, S100A9, and IL-36 $\gamma$ ; skin KLK5 activity; and circulating cytokines, such as IL-36 $\gamma$ , IL-1 $\beta$ , IL-4, IL-6, IL-8, TSLP, and TNF $\alpha$  and chemokines like CCL17 (TARC), CCL20 (MIP3A), CCL22 (MDC), and CCL27 (CTACK); and circulating IgE.

### **3. STUDY DESIGN**

#### **3.1. Overall Design**

##### **3.1.1. Overview**

This Phase 1b/2 study will enroll a total of 9 to 12 patients with NS and will be conducted entirely at 1 site in France, an NS center of excellence and referral which is expected to enroll NS patients with well-known disease histories at a relatively high rate.

It will be articulated in an Observational Part (12 weeks), during which patients will not be treated and will be investigated only to understand the course of their disease, an Interventional Part, during which patients will be treated with DS-2325a to understand its properties as a candidate drug product, and a Follow-Up, during which safety will be monitored after treatment.

The Interventional Part will be further articulated into 2 phases: A Main Phase (12 weeks) and an Extension Phase (24 weeks). The Interventional Part Main Phase is the core component of the study. It will be immediately and seamlessly preceded by the Observational Part and will be followed, also immediately and seamlessly, by the Interventional Part Extension Phase, as long as at the end of the Main Phase ECS is found as initial evidence of efficacy and warrants study continuation. All patients will transition from the Main Phase to the Extension Phase; however, the latter will be discontinued if ECS is not found. The Interventional Part Main Phase will be double-blinded and placebo-controlled: Patients will be randomized to 2 parallel arms to receive DS-2325a or placebo in a 2:1 ratio and will receive DS-2325a or placebo SC every other week, except for the initial (“loading”) dose, which will be administered by an IV infusion. The Extension Phase will be open-label and all patients will receive DS-2325a SC every other week. However, during both Main Phase and Extension Phase, a 600 mg SC dose will also be given one week after the first dose of the phase, coinciding with one week before following biweekly doses. Thus, eDS-2325a will be given at Weeks 1, 2, 3, 5, 7, 9, etc. Intravenous dose will not be given in Interventional Part Extension Phase. In case of patient(s) showing benefit from treatment with DS-2325a, the protocol of this study will be amended to allow a prolongation of the Extension Phase and, therefore, a continuation of DS-2325a administration within the clinical trial framework beyond the currently foreseen end. This should ensure that benefiting patient(s) will continue receiving cure.

The total study duration from first patient-in to last patient-out is expected to be 72 weeks, including Enrollment (expected to take 16 weeks), Observational Part (12 weeks), the entire Interventional Part, ie, both Main Phase (12 weeks) and Extension Phase (24 weeks), and Follow-Up (8 weeks). The duration including Enrollment, Observational Part, and the Interventional Part Main Phase, ie, until ECS readout, will be 40 weeks. Each patient will be involved in the study for the total of 56 weeks (12 weeks Observational Part + 12 weeks Interventional Main Phase + 24 weeks Extension Phase + 8 weeks Follow-Up), excluding up to 4 weeks of screening.

[figure not shown]
Study eligibility will be assessed at the beginning of the Observational Part and randomization for treatment will be done at the beginning of the Interventional Part, when eligibility will be re-confirmed. Randomization will follow a randomization schedule generated by a biostatistician independent of the study. Patients, investigators, and site staff will be blinded,

except for the unblinded site pharmacist or designee who will be responsible for preparing the study drugs. Sponsor's staff or representative (eg, clinical research organization) will also be blinded.

The DS-2325a dose has been selected based on the safety, tolerability, and PK results of the Phase 1a studies.

Replacing patients will be permitted during the Observational Part and the Interventional Part Main Phase in order to achieve a minimum of 9 patients for ECS evaluation at the end of the Interventional Part Main Phase.

**Figure 1: Study Design**

ECS = Early Clinical Signal

### 3.2. Discussion of Study Design

The intent of the Observational Part of the study is to gather ample information on the course of the NS disease of each patient participating in the study during the time immediately preceding study treatment administration. Based on clinical experience with NS patients, Observational Part 12-week duration, which matches the duration of the Interventional Part Main Phase, is thought to be adequate to gather this information. During the Observational Part, patients will be assessed according to the same safety and efficacy (including mechanistic efficacy) endpoints, as the Interventional Part Main Phase. This should give stronger possibility of comparing post-treatment with pre-treatment data than simply assessing patients once at Baseline, enhancing therefore the possibility to conclude if DS-2325a gives ECS or not. Additionally, the information collected during Observational Part will possibly be used to elaborate a mathematical disease progression model that could also facilitate concluding if DS-2325a gives ECS or not. Participation in the Observational Part should also give patients the possibility of acclimatizing with study environment and familiarizing with study procedures, such as use of questionnaires.

The intent of the Interventional Part of the study is to explore DS-2325a safety and efficacy, by comparing post-treatment with pre-treatment NS course and, in the Main Phase, the effect on NS of treatment with DS-2325a with treatment with placebo. Double-blind, placebo-controlled, and randomized design of the Interventional Part Main Phase should minimize bias. In addition to characterizing safety, intent of the Interventional Part Main Phase is to find ECS, as initial evidence of DS-2325a efficacy. Based on clinical experience with NS patients, Interventional Part Main Phase 12-week duration is thought to be adequate treatment time to find ECS, striking a balance between shorter times, which may not be sufficient for treatment to show effect, and

longer times, which may protract treatment to no avail. Early Clinical Signal will be inferred by the impact DS-2325a show on clinical endpoints, mainly IASI, and several mechanistic endpoints. Concomitant and consistent impact on multiple endpoints will represent ECS, especially if this impact is of large extent. This impact will be evinced by comparison of endpoint values between DS-2325a-treated and placebo-treated patients and especially between pre-treatment and post-treatment timepoints, since the Observational Part of the study should allow an in-depth characterization of each patient and thus facilitate pre-and post-treatment comparisons. Given its mechanism of action, there is an expectation that DS-2325a impact on endpoints will be unequivocally self-evident. However, in order to declare ECS finding, at least 50% of treated patients will have to achieve at least 50% decrease in total IASI score at the end of the Interventional Part Main Phase compared to Baseline. This is the minimum impact expected to be of clinical significance, which may justify DS-2325a use as a therapy for NS. The intent of the Interventional Part Extension Phase is to gather additional safety and efficacy information on DS-2325a, albeit under open-label design.

The intent of the Follow-Up component of the study is to monitor DS-2325a safety from the end of treatment, marked by the End of Treatment (EOT) visit, 1 week after the last drug administration, until the time DS-2325a is expected to have been virtually completely eliminated, marked by the End of Study (EOS) visit 8 weeks after EOT.

### **3.3. Stopping Rules**

#### **3.3.1. Subject-level Safety Stopping Rules**

For any subject experiencing the following events, treatment will be suspended until further evaluation by the Data Monitoring Committee (DMC).

- Any event severe in nature (eg, severe injection site reaction, severe allergic reaction, etc) deemed by the DMC as necessitating further safety review before treatment can be continued
- Hy's Law event: Alanine aminotransferase [ALT] or aspartate aminotransferase [AST]  $\geq 3 \times$  upper limit of normal [ULN] with simultaneous total bilirubin  $\geq 2 \times$  ULN)
- QTc prolongation: QT interval corrected with Fridericia's formula (QTcF)  $> 500$  msec OR increase in QTcF from pre-dose baseline of  $> 60$  msec

After an in-depth review of subject-level data is conducted by the DMC, one of the following recommendations will be made:

- To continue with treatment as planned
- To continue treatment, but at a reduced dose
- To terminate participation in the study

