#### **3.3.2. Population-level Safety Stopping Rules**

The DMC, as part of continuous monitoring of safety, will evaluate the data across the study for the following criteria:

- One active-treated subject experiences an AE of severe intensity (eg, severe injection site reaction, severe allergic reaction, etc) that is related to the study drug OR two active-treated subjects experience the same AE of moderate intensity that is related to the study drug.
- One active-treated subject with ALT or AST  $>5 \times$  ULN or serum total bilirubin  $>2 \times$  ULN.

If any of the above criteria are met, an in-depth review of data will be conducted by the DMC, and one of the following recommendations will be made:

- To continue with the study as planned, with no change
- To continue with the study as planned, with modification to the safety monitoring plan
- To continue with the study, but at a reduced dose
- To terminate the study

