## **5.8. Criteria for Discontinuing Study Drug**

Treatment will be temporarily put on hold until further evaluation by the DMC if the subject experiences

- Any event severe in nature (eg, severe injection site reaction, severe allergic reaction, etc) deemed by the DMC as necessitating further safety review before treatment can be continued
- Hy's Law event: ALT or AST  $\geq 3 \times$  ULN with simultaneous total bilirubin  $\geq 2 \times$  ULN)
- QTc prolongation: QTcF  $> 500$  msec OR increase in QTcF from pre-dose baseline of  $> 60$  msec

After an in-depth review of the safety data is conducted by the DMC, the decision to either continue with treatment as planned, to continue treatment, but at a reduced dose, or to terminate participation in the study will be made. If the decision is made to continue treatment, but at a reduced dose, the guidelines as specified in the dose reduction section of the protocol will be followed.

In addition, the subject will be discontinued from the study

- If a subject experiences a severe event or abnormal laboratory test result that the investigator deems to pose a safety risk if he/she were to continue in the study.
- If the use of prohibited medications such as topical corticosteroids and other topical immunosuppressive agents, including topical calcineurin inhibitors, or systemic corticosteroids, immunosuppressives, targeted therapeutics, biologics, and IV Ig is deemed necessary in the opinion of the investigator, the subject may be withdrawn to avoid biased interpretation of study results.
- If a subject shows worsening disease or lack of efficacy according to the discretion of the investigator.

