#### **8.5.5. Action Taken Regarding Study Drug**

- Dose Not Changed: No change in study drug dosage was made.
- Dose Reduced: The study drug dose was decreased.
- Drug Withdrawn: The study drug was permanently stopped.
- Drug Interrupted: The study drug was temporarily stopped.
- Not Applicable: The patient died, the study drug had been completed prior to a reaction/event, or the reaction/event occurred prior to the start of treatment.

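### The subject-level hold does not cover a related severe AE until the DMC has judged it, nor an isolated liver value that already opens study-wide review

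*Combined protocol and SAP*

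**What the plan says.** Section 3.3.1 suspends a patient's treatment until the DMC has evaluated the case, for three listed events. Section 5.8 repeats the list, introduced by "Treatment will be temporarily put on hold until further evaluation by the DMC if the subject experiences".

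- A severe event, with severe injection site and allergic reactions as examples, if it is "deemed by the DMC as necessitating further safety review before treatment can be continued".
- A Hy's Law event: ALT or AST ≥3×ULN together with total bilirubin ≥2×ULN.
- QTcF >500 msec, or a rise of >60 msec from pre-dose baseline.

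Section 5.8 also discontinues a patient after a severe event or abnormal laboratory result "that the investigator deems to pose a safety risk if he/she were to continue in the study".

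Section 3.3.2 sets study-wide triggers, which the DMC evaluates "as part of continuous monitoring of safety". One is "One active-treated subject experiences an AE of severe intensity", if related to study drug. Another is "One active-treated subject with ALT or AST" >5×ULN, or with total bilirubin >2×ULN. Each leads to a DMC review and a recommendation. The section does not say whether the patient concerned is dosed while that review runs.

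**The concern.** The severe-event hold is circular. It is meant to cover the wait for the DMC, yet it applies only to events the DMC has already judged. Until then no rule withholds the next dose.

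The liver rules leave a second gap. An isolated value can put the whole study under review while the patient who had it stays below the hold criterion, which needs both abnormalities at once.

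Safety is the primary objective. In these two cases a further dose depends on individual discretion or on how fast the DMC acts. For Hy's Law and QTcF it follows from a stated value. The protocol's own examples, severe injection site and allergic reactions, are events where dosing again before review is a real worry.

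**Working it through.** The plan states no figure on this point, so the check sets the rules side by side and then counts the dosing schedule.

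**1. What starts each subject-level hold (3.3.1, 5.8)**

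| Event | Starts on | DMC judgement needed first? |
|---|---|---|
| Severe event | DMC view that review is needed | Yes |
| Hy's Law | ALT or AST ≥3×ULN and bilirubin ≥2×ULN | No |
| QTcF | >500 msec, or rise >60 msec | No |

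**2. Liver values that open study-wide review but meet no hold**

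Hold: (ALT or AST ≥3) and (bilirubin ≥2), in multiples of ULN. Review (3.3.2): (ALT or AST >5) or (bilirubin >2). Review without hold occurs in two regions:

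- ALT or AST >5 with bilirubin <2, for example 8 and 0.5, or 20 and 1.9.
- Bilirubin >2 with ALT and AST <3, for example bilirubin 2.1 with ALT 1.

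Once ALT or AST is ≥3 and bilirubin is ≥2, the hold applies and there is no gap.

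**3. Reporting speed**

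The 24-hour list in 8.6 has four items: SAEs, combined liver abnormalities, pregnancy and overdose. A severe but non-serious AE is not on it, nor is a non-serious isolated liver value. Section 8.4 sends only serious injection site reactions through SAE reporting. Section 14.9 leaves the DMC's operating conditions to its charter.

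**4. Time to the next dose (Schedule of Events, Tables 1 and 2, footnotes 3 and 8)**

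Dose weeks are 1, 2, 3, 5, 7, 9, 11 (7 in the Main Phase) and 13, 14, 15, 17, 19, …, 35 (13 in the Extension Phase). That gives 7 + 13 = 20 doses and 19 intervals.

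- 7 days: after Weeks 1, 2, 13 and 14, so 4 intervals.
- 14 days: 19 − 4 = 15 intervals.

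Visit windows are ±1 day at Weeks 1, 2, 3, 13, 14 and 15, and ±2 days at the other dose weeks. If each visit may move within its own window:

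- 7-day intervals: 7 ± (1 + 1) = 5 to 9 days (4 of 19).
- Weeks 3–5, 11–13 and 15–17: 14 ± (1 + 2) = 11 to 17 days (3 of 19).
- The rest: 14 ± (2 + 2) = 10 to 18 days (12 of 19).

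Two of the short intervals follow the IV loading dose and the first SC dose. The other two fall at Weeks 13 to 15, when former placebo patients first receive active drug.

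**5. Time from a scheduled liver test to the next visit's dose**

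Five on-treatment tests are followed by later doses: Weeks 5, 9, 13, 21 and 29.

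- Week 13 to 14: 7 days (5 to 9 with windows).
- Weeks 5 to 7, 9 to 11, 21 to 23 and 29 to 31: 14 days each (10 to 18 with windows).

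**The case against.** The strongest reply is that the patient is not unprotected.

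- Section 5.8 already acts on the investigator's judgement, and the result is mandatory once that judgement is made.
- Section 8.5.5 lists "Drug Interrupted: The study drug was temporarily stopped" as an action, 5.4 provides for resuming afterwards, and 8.3 foresees stopping for liver enzyme abnormalities.
- Section 5.7.1 allows withdrawal for an AE or by physician decision. Sections 14.4 and 14.5 allow urgent measures against an immediate hazard.
- Dosing is supervised at one expert site, with AEs recorded before it.
- Many severe allergic reactions would be SAEs, and so reported within 24 hours.

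All of this is true, and it limits the likely harm. But each route is discretionary and none has a threshold, and reporting an event does not hold a dose.

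A second reply is that the proposed trigger also rests on judgement, since severity and causality are the investigator's call. That is right. However, 8.2 already requires both grades for every AE, so tying the hold to them makes it follow without a further decision.

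Third, 3.3.1 and 3.3.2 serve different purposes, and different thresholds are not in themselves an error. Section 3.3.2 also reacts to the same related moderate AE in two patients, and no hold is proposed for that. This stands in part: the liver change is the lesser of the two.

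Fourth, a hold lasts until the DMC answers, and the time that takes is not stated. That is a real cost, but the Hy's Law and QTcF holds already carry it.

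**Conclusion.** Both gaps are present in the current text. The severe-event wording is the more important. The liver point is a sound but smaller alignment of thresholds.

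For a severe AE just after a dose, the DMC or the investigator has nominally 7 or 14 days before the next one. This is the longest case, because a later onset leaves less time. The liver-test times assume the value becomes known too late to affect that day's dose, and a slow result shortens them.

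The number of extra doses cannot be derived, because the DMC's response time is in a charter that is not among the documents. It is 0 if the investigator or the DMC acts in time. The finding is therefore certain as to the wording and open as to the harm. The change is worth making because it is cheap and bears on the primary objective.

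**What to change.** In both 3.3.1 and 5.8:

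1. Start the temporary hold when the investigator grades an AE as severe (8.5.3) and related to study drug (8.5.4), pending DMC evaluation. Let the DMC still call for a hold after any other severe event.
2. Add as a hold trigger: ALT or AST >5×ULN, or total bilirubin >2×ULN.

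Apply both regardless of arm, because the investigator is blinded in the Main Phase. Leave the DMC's three possible recommendations as they are.

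The cost is one bullet reworded and one added in each of two sections. No visit, test or grading is added. The downside is an occasional delayed dose, including among the 7 Main Phase doses that precede the early clinical signal decision. With 2:1 allocation of 9 to 12 patients, only about 6 to 8 are on active drug in that phase. Limiting the severe-event trigger to related events keeps unrelated disease flares, and severe but minor events such as the headache mentioned in 8.5.3, from holding treatment. Trivial liver holds should be few, since screening criterion 4 in 4.2.1 already names much lower values (ALT and AST ≥2×ULN, total bilirubin ≥1×ULN) among its marks of excluded organ impairment.
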